1.0 Objectives

1.1 Study Objectives

The purpose of this study is to determine the most effective intraarticular steroid dose for the treatment of glenohumeral osteoarthritis. We aim to randomize patients into low, medium, and high dose groups of injectable corticosteroids as these doses are typically used in the standard of care for our patients. To date there has been no study to evaluate which dose is most efficient with the fewest side effects for glenohumeral osteoarthritis. Our objectives will be to provide ultrasound guided intraarticular glenohumeral injections of these randomized concentrations and to evaluate pain and function before and following injection with the Shoulder Pain and Disability Index (SPADI). We hypothesize that the low dose steroid will provide equivalent improvement of the pain and function to the medium and high doses, while minimizing side effects.

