3.3.2 Follow-up for withdrawn subjects

If a patient is withdrawn from the study, data collection will be terminated from that time point forward. All prior data collected will be included in the analysis. These subjects will not be

replaced, but instead more subjects may need to be enrolled. The new data will be recorded and analyzed as would any other new enrollee.

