8.0 Subject Numbers and Statistical Plan

8.1 Number of Subjects

Total number of subjects will be 171 allowing for 10% loss to follow-up.

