8.2 Sample size determination

This is a three arm trial comparing three different doses of steroid (20mg, 40mg, 80mg) in patients with glenohumeral arthritis. The primary endpoint is change in overall pain score on the SPADI at two, four, and six months from baseline. The sample size is determined based on assuming a minimal clinically meaningful difference in the 20mg vs 80mg groups as well as conducting non-inferiority tests in the 20mg vs 40mg and 40mg vs 80mg groups. Let d_1 , d_2 , and d_3 be the average change in overall pain scale for the three different doses (low, medium, high). For the first part, in the 20mg vs 80mg groups, we wish to have sufficient statistical power based on the assumption of a moderate Cohen effect size of .5 (e.g. differences of 40 vs 20 with a standard deviation of 40). This requires a sample size 51 per group based on a two-sided 80%-power 5%-level t-test. For the non-inferiority test, we assume d_1 , d_2 , and d_3 are 40, 36, and 32 (so $d_3-d_2=d_2-d_1=4$) with a standard deviation of 20. Allowing for a non-inferiority margin of 15 (so that differences less than 15 are deemed clinically non-inferior), a sample size of 52 per group based on an 80%-power 2.5%-level (since there are two tests) non-inferiority test (<http://powerandsamplesize.com/Calculators/Compare-2-Means/2-Sample-Non-Inferiority-or-Superiority>). Allowing for 10% loss to follow-up yields a final sample size calculation of **57 per group for each of the three groups**.

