8.3 Statistical methods

The primary endpoint is change from baseline of the shoulder pain and disability index (SPADI). The low dose and high dose changes will be analyzed with a two-sided two-sample t-test. Noninferiority tests with a margin of .5 will be used to test for a clinically meaningful difference between 20mg and 40mg doses and the 40mg and 80mg doses. The three groups will be summarized with descriptive statistics and univariate statistical tests using analysis of variance for normally distributed continuous variables, Kruskal-Wallis test for non-normally distributed continuous variables, and the Fisher's exact test for categorical variables. The demographic data and SPADI data will be analyzed accordingly. All statistical analyses, graphics, and reports will be prepared following best practices in conducting reproducible research in statistics utilizing various software packages built around the R software platform. [name]., Associate Professor, will serve as the Biostatistician for this study.

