16.2 Feasibility of recruiting the required number of subjects

Based on current patient volume we feel that we will have approximately 10-15 patients a month to recruit. We do not foresee an issue in recruitment since these injections are very common in these clinics in order to reach our total of 171 in order to have the study sufficiently powered

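### Section 8.2 claims 80% power for 20 mg versus 80 mg with 51 per group, but its stated inputs need 64, and 51 gives about 71%

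*Combined protocol and SAP*

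**What the plan says.** Section 8.2 sizes the trial on two calculations: a difference test for 20 mg versus 80 mg, and non-inferiority tests for 20 mg versus 40 mg and 40 mg versus 80 mg.

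The difference test is "based on the assumption of a moderate Cohen effect size of .5", with the example "differences of 40 vs 20 with a standard deviation of 40". The plan concludes: "This requires a sample size 51 per group based on a two-sided 80%-power 5%-level t-test". The non-inferiority calculation gives 52 per group. After an allowance for 10% loss to follow-up, the plan arrives at 57 per group.

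Section 8.1 carries this forward: "Total number of subjects will be 171 allowing for 10% loss to follow-up". Section 8.3 fixes the analysis: "The low dose and high dose changes will be analyzed with a two-sided two-sample t-test". Section 16.2 then relies on the total, speaking of recruitment "in order to reach our total of 171 in order to have the study sufficiently powered".

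**The concern.** Every input to the 20 mg versus 80 mg calculation is printed in section 8.2: effect size, sidedness, significance level, power and test. They can be put straight into the standard formula, and 51 is well below what the formula returns. The gap is 13 per group, too large to come from rounding or from using a normal approximation in place of the t distribution.

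This is one of the two calculations behind the sample size, and it concerns the primary endpoint. If 51 is wrong, the trial has less chance of detecting the stated difference than it claims, and the adequacy statement in section 16.2 is not true of this comparison.

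The direction of the error also matters. Section 1.1 says: "We hypothesize that the low dose steroid will provide equivalent improvement of the pain and function to the medium and high doses". The only direct test of 20 mg against 80 mg is the difference test, because the non-inferiority tests cover adjacent doses only. A non-significant result could be taken as support for the low dose, and a reader who believes power was 80% would give that result more weight than it deserves.

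**Working it through.** **Inputs (sections 8.2 and 8.3).** Difference 40 − 20 = 20 and SD 40, so d = 20/40 = 0.5. Two-sided α = 0.05, power 0.80, two equal groups, two-sample t-test. Stated result: 51 per group.

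**Required size, normal approximation.**
n = 2(z₀.₉₇₅ + z₀.₈₀)²/d² = 2(1.960 + 0.842)²/0.25 = 62.8, so 63 per group.

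**Required size, noncentral t** (noncentrality d√(n/2), 2n − 2 degrees of freedom): n = 63.77, so 64 per group. The stated 51 is not reproduced.

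**Can any variant give 51?**
- One-sided 5% (the same as two-sided 10%), 80% power: 50.15, so 51.
- Two-sided 5%, 70% power: 50.35, so 51.
- Two-sided 2.5%, 80% power: 77.31, so 78.

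The first contradicts the two-sided test in sections 8.2 and 8.3. The second contradicts the stated 80% power. The documents do not show how 51 was obtained.

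**Power actually delivered at d = 0.5, two-sided 5%.** Noncentrality at n = 51 is 0.5 × √25.5 = 2.52 on 100 degrees of freedom.

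| Evaluable per group | Power | Chance of missing the difference |
|---|---|---|
| 51 | 70.6% | 29.4% |
| 52 | 71.4% | 28.6% |
| 57 | 75.4% | 24.6% |
| 63 | 79.5% | 20.5% |
| 64 | 80.1% | 19.9% |

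A simulation of 200,000 trials with means 40 and 20 and SD 40 agrees: 70.5% at 51 per group and 75.6% at 57.

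**Does the final sample size repair it?** The non-inferiority figure does reproduce, with margin 15, assumed difference 4, SD 20 and one-sided α 0.025: n = 2 × 20² × (1.960 + 0.842)²/(15 − 4)² = 51.9, so 52. But 57 per group with 10% loss leaves 57 × 0.9 = 51.3 evaluable, or about 71% power for 20 mg versus 80 mg. With no loss at all, it is 75.4%.

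**Detectable difference at 80% power.** With 51 evaluable, d = 0.560, which is 0.560 × 40 = 22.4 points at the example SD rather than 20. With 57, d = 0.529.

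**Sensitivity to the other inputs in section 8.2, at 51 per group.** The non-inferiority calculation uses SD 20 and changes of 40 and 32 for the outer doses. That difference of 8 is d = 0.4, with power 51.6%. A difference of 20 with SD 20 is d = 1.0, with power 99.9%.

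**The case against.** The strongest case concedes the arithmetic and disputes its weight.

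- **Only the difference-test figure is wrong.** The non-inferiority figure, the larger of the two as printed, reproduces. That is so, but section 8.2 claims 80% power for both comparisons, and a correct figure for one does not supply power for the other. Had the plan used 64, that would have been the larger requirement.
- **The 29% is conditional.** Section 8.2 offers SD 40 only as an example and uses SD 20 elsewhere, so the trial's real power could be higher or lower. This stands as a limit on the 29%. It does not rescue the sentence, which is tied explicitly to d = 0.5.
- **More patients may be enrolled.** Section 3.3.2 says that after withdrawals "more subjects may need to be enrolled", with no stated cap. Against the total of 171 in section 8.1, the natural reading is that evaluable numbers go no higher than 57 per group, which is still short. This reading is an assumption, but an unquantified option does not make 51 correct.
- **No section says a non-significant 20 mg versus 80 mg result will be read as equivalence.** This is fair. Such a reading would be wrong at any power, so that risk is a possibility and not a stated plan. The misstated power stands without it.
- **Correcting the wording is not the only remedy.** The sponsor could resize instead: 64/0.9 = 71.1, so 72 per group and 216 in total. That option is real, but it means 45 more patients.

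**Conclusion.** The concern holds. On section 8.2's own inputs, the 20 mg versus 80 mg comparison needs 64 evaluable per group for 80% power, not 51. The planned size gives about 71% after the expected loss and at most 75.4% with none. The type II error at d = 0.5 is about 29% where 20% is claimed.

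The power figures assume d = 0.5, equal groups and a single unadjusted two-sided 5% comparison. What is established is that the stated size does not follow from the stated inputs. Power at the true effect and SD is unknown. The cause of the error is also unknown: a one-sided calculation would explain it, but that is inference.

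**What to change.** Replace the sentence in section 8.2 with one along these lines:

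> For 20 mg versus 80 mg, 51 evaluable patients per group give about 71% power (two-sided 5% t-test, single unadjusted comparison) for a standardised difference of 0.5, or about 75% if all 57 are evaluable. The difference detectable with 80% power at 51 per group is 0.56. Power of 80% at 0.5 would require 64 evaluable per group.

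In section 16.2, qualify the statement about adequate power by reference to this text.

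The change is to protocol wording only. Enrolment stays at 171, and no test or endpoint is altered. The cost is a less favourable power figure for this comparison. If the sponsor would rather keep 80% power at 0.5, the price is 216 − 171 = 45 more patients. At the 10 to 15 available a month given in section 16.2, that is at least 45/15 = 3 to 45/10 = 4.5 further months of recruitment.

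### The non-inferiority margin of 15 is not tied to any stated meaningful difference on a single SD, and passing both adjacent-dose tests does not establish that 20 mg is equivalent to 80 mg

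*Combined protocol and SAP*

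**What the plan says.** Section 8.2 has two calculations for the same endpoint.

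- **20 vs 80 mg.** "The sample size is determined based on assuming a minimal clinically meaningful difference in the 20mg vs 80mg groups". The section wants "sufficient statistical power based on the assumption of a moderate Cohen effect size of .5", and its example is a 20-point difference on SD 40.
- **Adjacent doses (20 vs 40, 40 vs 80).** Here "we assume d_1 , d_2 , and d_3 are 40, 36, and 32", "with a standard deviation of 20". Then: "Allowing for a non-inferiority margin of 15 (so that differences less than 15 are deemed clinically non-inferior". The result is 52 per group, "based on an 80%-power 2.5%-level (since there are two tests) non-inferiority test".

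Section 8.3 analyses low vs high dose with a two-sided two-sample t-test. It gives the margin of the adjacent-dose tests as .5, without a unit, and links it to a clinically meaningful difference. No section derives 15 from a minimal important difference, a placebo effect or a fraction of effect to be retained.

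The hypothesis in section 1.1 covers all three doses: "We hypothesize that the low dose steroid will provide equivalent improvement of the pain and function to the medium and high doses".

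**The concern.** A non-inferiority margin should be no larger than the loss one would mind. Section 8.2 names such a loss only in SD units (0.5), and then sets a margin that is 0.75 of the SD used to size the tests. If the 0.5 is carried to that SD, it is 10 points. A loss of 10 to 15 points would then be meaningful by one sentence and clinically non-inferior by another.

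The second problem does not need that conversion. The claim of interest spans 20 to 80 mg, but non-inferiority is tested only between neighbours, so two allowances of 15 points add up. The only direct 20 vs 80 analysis is a superiority t-test, which cannot establish equivalence when it is non-significant. The plan does not say which result governs if the tests and the t-test disagree. At stake is the trial's main message, that the low dose works as well as the higher ones.

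**Working it through.** **Inputs (section 8.2):** margin 15; SD 20 for the non-inferiority tests; assumed adjacent difference 4, taken against the lower dose; level 2.5%, taken as one-sided; power 80%; benchmark 0.5 SD, with the example of 20 points on SD 40.

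**Reproducing the plan's figure.** n = 2 × [20 × (1.960 + 0.842)/(15 − 4)]² = 51.9, so 52 per group. This matches the plan.

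**Margin against benchmark.**

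| SD used | Margin 15 in SD units | 0.5 SD in points | Margin wider than 0.5 SD? |
|---|---|---|---|
| 20 | 15/20 = 0.75 | 10 | yes |
| 40 | 15/40 = 0.375 | 20 | no |

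**Two steps.** If each loss is shown only to be below 15, the 20 vs 80 loss is shown to be below 15 + 15 = 30. That exceeds both 10 and 20.

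**Chance of passing one test.** SE = 20 × √(2/52) = 3.92, and P(pass) = Φ((15 − loss)/3.92 − 1.96).

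- loss 4: Φ(0.85) = 0.80
- loss 8: Φ(−0.18) = 0.43
- loss 10: Φ(−0.69) = 0.25

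**Chance of passing both.** The tests share the 40 mg arm, so their statistics have correlation −0.5. Bivariate normal results at SD 20:

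| True 20 vs 80 loss | Split | Both pass |
|---|---|---|
| 10 | 5+5 | 47% (46% simulated with t-tests) |
| 10 | 7+3 | 42% |
| 10 | 10+0 | 22% |
| 20 | 10+10 | 1.7% |

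**Adding the planned 20 vs 80 t-test.** In simulation of the 5+5 case the t-test finds 20 mg significantly worse in 71% of trials. The 46% in which both non-inferiority tests pass divides into about 23% with that t-test significant and about 23% with it non-significant.

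**What the data show when both tests pass.** A pass needs an observed loss below 15 − 1.96 × 3.92 = 7.3 per step. The observed 20 vs 80 loss is then below 14.6, and its upper 95% limit below 14.6 + 7.7 = 22.3 points. This is tighter than 30, but it still does not guarantee exclusion of 10 or 20 points.

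**Power if the margin is 0.5 SD on SD 20 (10 points), 52 per group.**

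- 4-point deficit for the lower dose: Φ(6/3.92 − 1.96) = 0.33 per test
- no deficit: Φ(10/3.92 − 1.96) = 0.72 per test
- lower dose better by 4: Φ(14/3.92 − 1.96) = 0.95 per test

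**The case against.** A reader might infer that the protocol sets a 10-point threshold and then exceeds it. The documents do not support that. Ten points appears nowhere in them; it comes from multiplying the .5 of one calculation by the SD of the other. The only example in points is 20, and 15 is below 20. A meaningful difference fixed in points would not halve because another calculation assumes a smaller SD. This objection stands, so the 10-to-15-point contradiction is conditional.

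Section 8.3 may already hold a tighter margin. If its .5 means 0.5 SD, the analysis margin equals the benchmark and the contradiction does not arise. The fault is then that the trial was sized for another margin, with 33% power at the assumed deficit instead of 80%. Nothing shows which margin is operative.

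The direct t-test also matters. A reader might take 47% as the chance of an unopposed wrong claim of equivalence. With the t-test counted, about 23% is the share with no significant result against 20 mg, and only if the true loss is 10 points split evenly at SD 20. At SD 40 the same 5+5 loss passes both tests in 1.7% of trials.

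Nor can one say that the 80% power exists only because the margin is too wide. As written, d_1 = 40 and d_3 = 32, so d_3 − d_2 is −4, not 4. If d is improvement, the lower dose is assumed better, and a 10-point margin would give 95%.

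The stacking point survives as a limit on what two passes establish by themselves. The data will usually show more: 22.3 points at worst at SD 20. At SD 40 the same arithmetic (SE 7.84) gives 2 × (15 − 15.4) + 15.4 = 14.6, which excludes 20 points, but power per test at the 4-point deficit is then only 29%. This is a reason to report the 20 vs 80 interval directly.

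**Conclusion.** The concern holds in a limited form. The margin of 15 is unjustified, section 8.2 uses two SDs for one endpoint, and section 8.3 gives a different margin. Whether 15 is wider than the plan's meaningful difference cannot be settled from the documents: it is on SD 20, and it is not on SD 40 or in the points of the example.

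On either SD, passing both adjacent-dose tests bounds the 20 vs 80 loss only at 30 points and so does not by itself support the hypothesis of equivalent improvement. If the true loss is 10 points split evenly (52 per group, SD 20, one-sided 2.5% per test), both tests pass in about 46-47% of trials. In about 23% of trials the report would call 20 mg significantly worse than 80 mg and also clinically non-inferior at each step. If the true loss is 20 points (10+10), both pass in under 2%, so large losses are unlikely to slip through.

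**What to change.** In sections 8.2 and 8.3, state one SD, one meaningful difference in SPADI points, and one margin in the same points that is no wider than it, with the reason for it. State the direction of the assumed 4-point difference. Restate the power for that margin. If it is 0.5 SD on SD 20, that is 33% per test at a 4-point deficit for the lower dose and 72% at no deficit, with 52 per group. A 10-point margin is one option; the documents give no clinical basis for imposing it.

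If 15 is kept, delete the clause that labels smaller differences clinically non-inferior, and report a pass only as a loss of less than 15 points per dose step. Report the 20 vs 80 confidence interval against the stated meaningful difference. Call 20 mg equivalent or clinically non-inferior only when that interval excludes a loss of that size. The interval is worth reporting under any margin, because two steps always add to twice the margin.

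The cost is wording, with no extra patients or procedures. The downside is a less favourable stated power or a weaker permitted claim. Restoring 80% power at a 10-point margin is a separate choice: 2 × [20 × 2.802/6]² gives 175 per group before dropout at a 4-point deficit, and 2 × [20 × 2.802/10]² gives 63 at no deficit.

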8.3 Statistical methods

The primary endpoint is change from baseline of the shoulder pain and disability index (SPADI). The low dose and high dose changes will be analyzed with a two-sided two-sample t-test. Noninferiority tests with a margin of .5 will be used to test for a clinically meaningful difference between 20mg and 40mg doses and the 40mg and 80mg doses. The three groups will be summarized with descriptive statistics and univariate statistical tests using analysis of variance for normally distributed continuous variables, Kruskal-Wallis test for non-normally distributed continuous variables, and the Fisher's exact test for categorical variables. The demographic data and SPADI data will be analyzed accordingly. All statistical analyses, graphics, and reports will be prepared following best practices in conducting reproducible research in statistics utilizing various software packages built around the R software platform. [name]., Associate Professor, will serve as the Biostatistician for this study.

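### The non-inferiority tests are sized on a margin of 15 (section 8.2) but specified with a unitless margin of .5 (section 8.3), so the stated 80% power does not apply to the test that would be run

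*Combined protocol and SAP*

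**What the plan says.** All of this is in the combined protocol and SAP.

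- **Section 8.2, margin:** "Allowing for a non-inferiority margin of 15 (so that differences less than 15 are deemed clinically non-inferior".
- **Section 8.2, assumed means and SD:** "we assume d_1 , d_2 , and d_3 are 40, 36, and 32 (so $d_3-d_2=d_2-d_1=4$) with a standard deviation of 20".
- **Section 8.2, result:** "a sample size of 52 per group based on an 80%-power 2.5%-level (since there are two tests) non-inferiority test". Allowing 10% for loss to follow-up, the plan recruits 57 per group.
- **Section 8.2, the separate 20 vs 80 mg superiority comparison:** this is sized on "a moderate Cohen effect size of .5 (e.g. differences of 40 vs 20 with a standard deviation of 40". It is the only other place in the statistical sections where .5 appears.
- **Section 8.3, analysis:** "Noninferiority tests with a margin of .5 will be used to test for a clinically meaningful difference between 20mg and 40mg doses". The sentence goes on to cover 40 vs 80 mg. No unit is attached to .5.
- **Section 1.1, hypothesis:** "We hypothesize that the low dose steroid will provide equivalent improvement of the pain and function to the medium and high doses".

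Nothing in the documents links .5 to 15 or says which governs.

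**The concern.** The margin is the decision rule of a non-inferiority test, and the plan gives two for the same pair of comparisons. The trial is sized on the one in section 8.2, but an analyst would follow section 8.3. These two tests carry the non-inferiority claims behind the hypothesis in section 1.1, so a change of margin can change the trial's main message.

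Because .5 has no unit, it can be read as stricter or looser than 15. If that is settled after the data are seen, the choice is open to challenge as post hoc. Section 8.3 also describes the tests as looking for a clinically meaningful difference, which is the reverse of what a non-inferiority test concludes.

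**Working it through.** **Inputs.** Margin 15, SD 20, adjacent difference 4, 80% power, 2.5% level and 52 per group come from section 8.2, as do Cohen .5 and the illustrative SD of 40. Margin .5 comes from section 8.3. Below, deficit means the amount by which the lower dose is truly worse. z(.975) = 1.960 and z(.80) = 0.8416, summing to 2.8016.

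**1. Reproduce the plan's 52.** n per group = 2 × [2.8016 × SD / (margin − deficit)]².

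With 15, 4 and 20: 2 × (2.8016 × 20 / 11)² = 51.9, so 52. The direction matters: no true difference gives 28, and a 4-point advantage for the lower dose gives 18. The plan does not state the direction in words; a 4-point deficit is inferred because only it reproduces 52.

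**2. Try to reconcile the margins.** .5 × 20 = 10 and .5 × 40 = 20. For .5 SD to equal 15, the SD would have to be 15 / .5 = 30, which is printed nowhere. Power at margin 15 and SD 30 with 52 per group would be 46%.

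**3. Power at 52 per group.** Power = Φ[(margin − deficit) / (SD × √(2/52)) − 1.960], deficit 4. The standard error is 3.922 at SD 20 and 7.845 at SD 40.

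| Reading | Margin (points) | SD | Power | n per group for 80% |
|---|---|---|---|---|
| Section 8.2 | 15 | 20 | 80.1% | 52 |
| .5 SD at SD 20 | 10 | 20 | 33% | 175 |
| .5 SD at SD 40 | 20 | 40 | 53% | 99 |
| .5 scaled by SD 40, tested at SD 20 | 20 | 20 | 98% | 25 |
| .5 points | .5 | 20 | 0.2% | none (deficit exceeds margin) |
| .5 points | .5 | 40 | 0.8% | none |

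For example, the second row is Φ(6 / 3.922 − 1.960) = Φ(−0.430) = 0.33. A noncentral t calculation agrees within one percentage point.

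**4. Effect on the decision at SD 20.** The largest observed deficit that still passes is margin − 1.960 × 3.922 = margin − 7.69.

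- Margin 15: 7.3 points.
- Margin 10: 2.3 points.
- Margin 20: 12.3 points.
- Margin .5: −7.2, so the lower dose would have to look at least 7.2 points better.

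With a true 4-point deficit, the chance that one comparison passes margin 15 and fails margin 10 is 0.801 − 0.334 = 0.467. The chance that it passes margin 20 and fails margin 15 is 0.983 − 0.801 = 0.182.

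**5. Dependence on the assumed deficit.** With no true difference, .5 SD gives 72% power at either SD. If the lower dose were truly 4 points better, it gives 95% (SD 20) or 86% (SD 40).

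**6. Two secondary points, neither of which changes the 52.**

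- *SD.* Section 8.2 illustrates the superiority effect with SD 40 and then assumes SD 20. The superiority sample size depends only on the ratio, so nothing breaks there. If SD 40 applied to the non-inferiority tests, power at margin 15 would be Φ(11 / 7.845 − 1.960) = 29%. If SD 20 applies throughout, a Cohen .5 effect is 10 points, inside the margin of 15, and a true 10-point loss would be declared non-inferior with probability Φ(5 / 3.922 − 1.960) = 25%. In the illustration as printed, the difference is 20 points and the margin lies below it.
- *Sign.* Means of 40, 36 and 32 for low, medium and high give d_3 − d_2 = 32 − 36 = −4, not the printed 4.

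**The case against.** The strongest reply is that section 8.2 gives an explicit rule, the 52 reproduces exactly, and .5 is probably the Cohen value carried into the wrong sentence. If so, correcting one number settles the matter and the sample size is untouched. That may be right, but the documents do not say it, and section 8.3 is the text that governs the analysis. A likely slip in the decision rule still has to be corrected.

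Three further objections have force and limit what can be claimed.

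- **The error need not reduce power.** Scaling .5 by SD 40 and testing at SD 20 uses only printed figures and gives 98%. The sound statement is that power depends on an unstated unit and is 80% under none of the readings. The 98% reading achieves its power with a looser rule, so it is no reassurance.
- **The 4-point deficit is inferred.** The printed means, if they are improvements, point the other way, and .5 SD would then have more than 80% power. The deficit stands as the sizing assumption because it alone yields 52.
- **The 47% disagreement belongs to the 10-point reading.** Under the 20-point reading at SD 20 it is 18%, in the opposite direction.

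It is also fair that section 8.2 attaches no unit to 15. Points on the SPADI is the natural reading, but sections 1.2 and 8.3 refer to the SPADI overall while section 8.2 refers to a pain score. The calculations under mixed SDs are hypothetical and carry little weight in the conclusion.

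**Conclusion.** The concern holds. Sections 8.2 and 8.3 give different margins for the same two tests, neither printed SD converts one into the other, and the 80% power belongs only to margin 15 with SD 20.

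At 52 evaluable per group, one-sided 2.5% and a true 4-point deficit, the section 8.3 test has 33% or 53% power if one SD is used throughout and .5 means SD units. It has 98% under the mixed reading and under 1% if .5 means points. The shortfall is specific to the deficit the sample size implies; the contradiction between the decision rules does not depend on it. The plan is wrong as written here, and it must be corrected before the non-inferiority results can be interpreted.

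**What to change.** Before unblinding:

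1. State one margin, in points on a named SPADI score, in both sections 8.2 and 8.3. If 15 is intended, replace .5 in section 8.3 with 15 SPADI points.
2. State one SD for the change score, and check the margin against the difference the plan regards as minimally meaningful.
3. State the assumed means and the direction of benefit so that they agree with the 4-point difference.
4. Reword section 8.3 so that the tests conclude non-inferiority.
5. If any margin or SD other than 15 and 20 is adopted, replace the 80% with the power that follows at the planned size.

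**Cost.** If 15 and SD 20 are kept, this is protocol wording only. If .5 SD is intended with one SD throughout, either the power is restated as 33% (SD 20) or 53% (SD 40), or the evaluable number per group rises from 52 to 175 or 99. A 20-point margin at SD 20 would need no more patients, but it is looser than the margin the trial was sized on and would need its own justification.
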